7.0 Setting

All aspects of this study will take place using virtual MUSC communication platforms means such as telephone, email or a meeting platform such as MS Teams. Initial study procedures (consent, basic demographic questionnaire and baseline measures) and subsequent visit measures will be completed remotely using REDCap survey. Post-intervention interviews will be conducted virtually. Participants will be able to participate in this study in the comfort and privacy of a setting of their own choosing.

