10.0 Study Design / Methods

Intervention activities include delivering the intervention materials with up to 30 PWD/CG dyads with measurement of feasibility, process, and outcomes. Thirty enrolled PWD/CG dyads will be provided with the SUPPORT-D written materials, an electronic pdf of the SUPPORT-D booklet and links to electronic videos reviewing the content of the written booklet. Participants will be provided the option to utilize their personal mobile device to access digital content and MS Teams to determine which is method is preferred (print or digital) and to facilitate sharing of intervention materials with family members at a distance unable to review print materials. For those that do not have access to a personal mobile device a mobile device (tablet) with the digital content preloaded and MS Teams preloaded for use throughout the study period. Following consent and study enrollment, baseline measures will be completed electronically by participants via an email link or verbally by the PI or research assistant (RA). This is followed by an orientation visit with the PI or RA where participants will receive intervention materials, orientation for accessing digital material, instructions for sharing digital resources with friends and family and detailed instructions on how to access the video conferencing software MS Teams from the personal device/provided tablet for study visits and a support number to call for technical assistance if necessary. Participants will retain the device and printed materials for the length of the study. Participants will be asked to return provided tablet devices at the end of the 8-week study period. However, participants will retain printed materials and identical digital materials at the end of the study period. The first virtual study visit via telehealth (e.g., MS Teams) with the nurse interventionist will be scheduled within 1 week of receiving tablet device/orientation. During this first virtual study visit the SUPPORT-D intervention will be delivered via MS-Teams for approximately 60 minutes by the nurse interventionist using a manual for guidance and recorded for fidelity monitoring. To ensure standardized content is provided the nurse interventionist will respond to questions by referencing the provided materials. If questions go beyond content, the interventionist will advise patients to consult their provider and assist the PWD/CG dyad in crafting questions that address additional concerns. The focus of this visit will be to provide an overview of the intervention, review detailed content for the first two parts of the intervention (understanding the disease and caring for myself) and provide participants instruction in maintaining an electronic or paper self-report log of home use of SUPPORT-D materials including when, what and how (format), content was reviewed and if shared with others (who, when, feasibility). Dyads will be encouraged to review these materials at home and share information with other family members. The PI will conduct fidelity monitoring for 10% of all study visits. Two weeks after the first virtual study visit dyads will be scheduled for a second virtual study visit via with nurse interventionist for delivery of parts 3 and 4 (information for the caregiver and planning for the future) of the intervention via MS Teams and recorded for fidelity monitoring. This session should last approximately 60 minutes. The nurse interventionist will utilize a manual for guidance to tailor study visit discussions according to baseline data collection, emphasizing areas of evident knowledge deficit based on questionnaire responses. All participants will

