
Figure 2. Intervention Delivery Timeline

attend a virtual post-intervention meeting (study week 8) with the PI via MS-Teams during which post-intervention data will be collected and a time scheduled for returning the tablet device. The PI will meet with the nurse interventionist weekly during the intervention. Each dyad will receive the SUPPORT-D intervention for a span of six-weeks with a two-week post intervention follow up (8-week total study period). The timeline for intervention delivery is also described in Table 2.

Post-intervention interviews. At the conclusion of the study period all dyads (30 dyads) will be asked their willingness to participate in post-intervention key informant interviews. Of those that express a desire to participate 10 dyads will be randomly selected via computer to participate in a post intervention interview with the PI to obtain more in-depth feasibility data related to accessibility, usability, and adherence to the intervention. A qualitative descriptive approach will be used to conduct the semi-structured interviews, which will last 45-60 minutes. An interview guide with open-ended questions and probes will be used to guide the semi-structured interview. Interviews will be recorded for the purposes of transcription for data analysis.

Table 2: Variables for Aims 1 and 2

McMillan Good Death Model Domain and major tasks	Measure/Instrument/ Psychometrics/Instrument scoring	Data sources and time points
Fixed characteristics of the patient		
Demographics/clinical characteristics	Age, gender, race, education, health history, date of diagnosis, diagnosis, # comorbidities	PWD/ CG, baseline
Modifiable dimensions of patient experience		
Knowledge	Alzheimer's Disease Knowledge Scale (ADKS), 30-items (TF), Cronbach's alpha .80 ²³ , summed total of correct items	PWD/CG, baseline and post-intervention
Acceptability of Intervention	Acceptability of Intervention Measure (AIM), 4 items; Cronbach's alpha 0.75-0.90 ²⁴ , calculated mean	PWD/CG, post-intervention

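### The ten feasibility interviews are an unstratified random draw from volunteers, so by chance they may include few or none of the dyads whose access or attendance trouble they are meant to explain

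*Combined protocol and SAP*

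**What the plan says.** The post-intervention interviews paragraph of Section 10.0 sets the frame and the rule. The frame is broad: "At the conclusion of the study period all dyads (30 dyads) will be asked their willingness to participate in post-intervention key informant interviews". The rule is a simple random draw: "Of those that express a desire to participate 10 dyads will be randomly selected via computer to participate in a post intervention interview". The aim is "to obtain more in-depth feasibility data related to accessibility, usability, and adherence to the intervention". No stratum, quota or purposive criterion is given.

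The information needed for a more targeted draw is already planned. Table 2 lists the number of times a participant could not reach the digital materials or the meeting software, and the Statistical Analysis Plan paragraph defines adherence as attendance at every study visit.

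On mode, Section 7.0 says "Post-intervention interviews will be conducted virtually", and the virtual means it lists are "telephone, email or a meeting platform such as MS Teams". On equipment, Section 10.0 provides tablets as follows: "For those that do not have access to a personal mobile device a mobile device (tablet) with the digital content preloaded". It then says "Participants will be asked to return provided tablet devices at the end of the 8-week study period", and at the week-8 meeting "post-intervention data will be collected and a time scheduled for returning the tablet device". No interview date is stated.

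**The concern.** The counts in Table 2 will show that access failures or missed visits occurred. The interviews are the planned source for explaining why. The dyads best placed to explain are those that had the trouble, and they may be few. A draw that ignores this lets chance decide whether any of them is heard.

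If none or only one is drawn, the qualitative findings will rest mainly on dyads for whom delivery went smoothly. Section 1.0 says the study is to inform a later randomized trial, so a thin account of the barriers weakens one of its main products. Nothing is gained in exchange: the interview data go to directed content analysis, and no planned estimate depends on the interviewees being a simple random sample.

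**Working it through.** There is no plan figure to reproduce. The ten interviews and up to 30 dyads are stated without a calculation, and the sample size paragraph says none was performed. The check is therefore an illustration.

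**Inputs**
- Interviews drawn: 10 (Section 10.0).
- Willing dyads, N: not given; at most 30. As one alternative, 2 dyads weekly over three months, taken as 13 weeks, gives 2 × 13 = 26.
- Willing dyads with a missed visit or access failure, K: not given. A range is shown.

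**Formulas** (draw without replacement, where C(a,b) is the number of ways to choose b from a)
- P(none) = C(N−K, 10) / C(N, 10)
- P(exactly one) = K × C(N−K, 9) / C(N, 10)
- Expected number drawn = 10K/N

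**Two cases written out**
- N = 30, K = 3: P(none) = (20×19×18)/(30×29×28) = 6,840/24,360 = 0.281. P(one) = 3×10×(20×19)/24,360 = 11,400/24,360 = 0.468. At most one: 0.749.
- N = 26, K = 4: P(none) = (16×15×14×13)/(26×25×24×23) = 43,680/358,800 = 0.122. P(one) = 4×10×(16×15×14)/358,800 = 134,400/358,800 = 0.375. At most one: 0.496.

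**Range**

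| Willing N | With trouble K | Expected in 10 | P(none) | P(at most one) |
|---|---|---|---|---|
| 30 | 3 | 1.0 | 0.281 | 0.749 |
| 25 | 3 | 1.2 | 0.198 | 0.654 |
| 20 | 3 | 1.5 | 0.105 | 0.500 |
| 26 | 4 | 1.5 | 0.122 | 0.496 |
| 30 | 6 | 2.0 | 0.065 | 0.326 |
| 26 | 8 | 3.1 | 0.008 | 0.081 |
| 30 | 9 | 3.0 | 0.012 | 0.100 |

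The risk is material when trouble is uncommon and small when about a third of willing dyads had it.

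**If dyads with trouble volunteer less often.** Assume 30 dyads, 6 with trouble, volunteering at 50% against 80% for the rest. Averaging the same formula over binomial volunteering gives 0.195 for none and 0.597 for at most one, compared with 0.065 and 0.326 when volunteering is equal.

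**Under a stratified draw.** With places reserved for the first stratum, none is interviewed only if none volunteers. In the same case that is 0.5^6 = 0.016 instead of 0.195. With 3 such dyads it is 0.5^3 = 0.125 instead of 0.476. The remaining risk is non-volunteering, which no selection rule removes.

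**The case against.** The best defence is that a computer draw is unbiased among volunteers and keeps the investigator, who conducts the interviews, from choosing the interviewees. That stands, and it is a reason to keep the computer and add strata, not to move to hand-picking. It is also true that if trouble is common, a plain draw will rarely miss it (1.2% for none at 9 of 30; 0.8% at 8 of 26), and that strata drawn from volunteers do not cure self-selection.

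Access and adherence are also measured outside the interviews: access failures and the feasibility and appropriateness scales in Table 2, attendance and calls for assistance in the Statistical Analysis Plan paragraph, use logs, and the weekly contact in Section 13.0. The occurrence of trouble is therefore not lost; only its explanation is at risk. The second interview, on the digital version, helps little, because it is limited to those who complete the study and uses the same process.

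A reader might infer more than the documents support:
- **That dyads using a study tablet are shut out because tablets go back before a virtual interview.** Section 7.0 counts the telephone among the virtual means, Section 12.0 has interviews captured on audio recorders, no interview date is given, and week 8 only sets a time for return. Participants also keep the printed booklet, which has the same content.
- **That people who took part alone under Section 6.0 are excluded because only dyads are drawn.** The protocol uses that word for enrolled units generally, including for visits and payment. Their eligibility needs a clarifying phrase; an exclusion is not shown.
- **That non-completers are barred from the first interview.** The text says all dyads are asked. However, Section 14.0 allows withdrawal for missed visits and no exit contact is described, so the least adherent may be gone when the question is put.

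**Conclusion.** The point holds as an inexpensive improvement to a design choice. The selection rule ignores information the study already collects on the very topics the interviews are to explain. If 3 or 4 of 25 to 30 willing dyads had trouble, the chance of hearing from none is 12% to 28%, and from at most one 50% to 75%. At 9 of 30 the chance of none falls to 1.2%. These figures depend on assumed values of N and K, and on every selected dyad actually being interviewed. Lower volunteering among dyads with trouble would raise the risk. The evidence does not show that the draw is biased, that tablet users cannot be interviewed, or that the barriers would go unrecorded.

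**What to change.** In Section 10.0, keep ten computer-drawn interviews and add the following.
- Form two strata among willing participants: any missed study visit or logged access failure, versus neither. Draw up to five from the first and the rest from the second; if either stratum is short, fill from the other.
- State that people who took part alone are eligible units.
- Enrolment is rolling (1 to 2 dyads weekly over three months), so a single draw cannot be made at each dyad's week-8 meeting. Either draw once the list of willing participants is complete, or fill the strata as participants finish, under a computer rule fixed in advance.
- Offer the telephone, which Section 7.0 already allows, to anyone whose tablet has been returned. No tablet then has to be held back, which matters because the sample size paragraph names device availability as a constraint.

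The cost is a few sentences, with the same number of interviews. The downside is that the ten interviewees no longer mirror the volunteers proportionally. The first stratum is over-represented when it is small, and if it makes up more than half of the volunteers, five of ten is below its share (10K/N exceeds 5 when K exceeds N/2). Report the stratum sizes with the findings, and state as a limitation that dyads that decline or withdraw are not reached.

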12.0 Data Management

Data Capture and Management. This study will use Research Electronic Data Capture (REDCap) for data capture and management. REDCap is a software toolset and workflow methodology for the electronic collection and management of research and clinical trials data. REDCap provides secure, web-based, flexible applications, including real-time validation rules with automated data type and range checks at the time of data entry. Exports are made available for several statistical packages including SPSS, SAS, SATA, R and Microsoft Excel. The study-specific REDCap database will be designed and developed by MUSC research team. The provision of REDCap is made available through the South Carolina Clinical & Translational Research (SCTR) Institute at MUSC with NIH Grant awards UL1RR029882 and UL1TR000062.

Participant screening and enrollment-Data from participants screened for study enrollment will be entered into an electronic study database. Designated research staff will collect, gather, and enter required data (written informed consent, medical history, and demographics) onto study data forms. Screened patients who do not meet study eligibility will have specific screening data entered in the study database. The collected data will be helpful in examining the patient population and feasibility of enrollment criteria and will include gender, age, race, and reason for exclusion. All dates will be shifted, and other Personal Health Information (PHI) will be removed from the study database upon study completion. All data obtained from this study will be used for research purposes only and will comply with Federal HIPAA regulations. Master Screening and Enrollment Logs will be maintained electronically and will be used to prepare reports on accrual and attrition for the PI and SMC.

Case report forms-This study will utilize electronic case report forms (e-CRFs). All study specific e-CRFs will be designed by the PI or PC and transferred for use in the study's centralized REDCap database. These study specific eCRFs (study logs for correspondence, compensation, and other forms such as pre-eligibility screens) will be coded by the participant's unique study ID# for all data collected and will be maintained within the participant research record.

Binders-The PC will maintain a unique electronic study record for participants containing all eCRFs records. A regulatory e-file will also be maintained to include the IRB-approved Protocol, original Informed Consent documents, and other study-related regulatory documents. Access to the research record, (study database and PHI's) will be restricted to study personnel as approved by the PI and MUSC IRB. As with all studies conducted at MUSC, this study is also eligible for a random audit by MUSC Office of Compliance.

Data security-Ensuring data security, compliance with 45 CFR 46 and maintaining the integrity of PHI is a top priority. MUSC has Standard Operating Procedures (SOP) to ensure a high level of data security while coordinating electronic and paper data management activities for clinical research trials. The REDCap study database will be hosted in the Biomedical Informatics secure data center at MUSC, a secure environment for data systems and servers on campus, and includes firewall, redundancy, failover capability, backups, and extensive security checks. The secure data center has strict access control; only authorized core personnel may access the facility un-escorted. Only authorized users are allowed to connect to the network, and the security of the network is actively monitored. Power and environmental controls have several layers of backups, from interruptible power supplies to alternate and redundant feeds to the local utility company. The REDCap system administrator contributes to the maintenance of institutional disaster recovery and business continuity plans. Load balancers and a highly fault tolerant SAN infrastructure contribute to high availability.

Data entry-Only MUSC IRB approved study personnel that are authorized to have access to the REDCap study database will be granted password access. Study personnel using computers that are connected to the Internet will directly enter data into the remotely housed database. As such, no electronic study data will be stored on hard drives and/or any portable electronic devices. Additionally, all personnel with access to the database will have current University of Miami CITI training in the Conduct of Human Subject Protections, and Good Clinical Practice (GCP) training in the Conduct of Human Subject Protections, and HIPAA and Information Security trainings that are completed annually. Each participant will be assigned a unique study identifier, all PHIs will be masked, and data exports will be limited to the PI, the PC, and the BS for generating reports and the conduct of statistical data analysis.

Data monitoring-The PI or PC will conduct routine monitoring of the study database and generate a report for the PI to review at study team meetings. Standing agenda items for these meetings will include participant recruitment and retention, AE's, protocol deviations, data integrity and overall study conduct. The PI will work with the PC to resolve and validate discrepant data. Discrepancies that warrant clarification will be sent to appropriate parties for review and resolution. All data entry and changes made in the study database by authorized study personnel will be automatically logged by REDCap and provide a transparent visible audit trail for reviewers. Protocol deviations will be reported by the PI in accordance with Institutional policy.

Audio Recordings and Transcriptions: Participant interviews will be recorded using audio voice recorders. Audio recordings will be uploaded for transcription within 48 hours to an outside agency with which MUSC has established a Business Associates Agreement (BAA). Once uploaded, all audio recordings will be deleted from the portable storage device. The recorded interview will then be immediately erased from the portable voice recorder. Transcription will only include the study ID number without PHI. Interview transcriptions will be stored in a standard file format in REDCap. Research staff will conduct daily checks of data transfer. A linkage file for the study ID number and PHI will be maintained in a password-protected server behind the MUSC firewall in order to link the questionnaire and interview data.

13.0 Provisions to Monitor the Data to Ensure the Safety of Subjects

The PI, [name] will be responsible for the overall monitoring of the safety of the study and the Program Coordinator (PC) [name] will be responsible for the daily monitoring and safeguarding of study data to ensure the safety and protection of all human study participants. [name] will report observed and solicited adverse events, and protocol deviations to [name]. [name] will be responsible for the classification of all reported adverse events (AE) and for ensuring that all serious adverse events (SAE), protocol deviations, and 'other' reportable events are forwarded to MUSC IRB in compliance with institutional policies and procedures. [name] will also be responsible for maintaining the electronic

regulatory binder, ensuring data management validation and verification of the electronic study research database.

Monitoring Study Safety. From initial screening of study participants utilizing inclusion and exclusion criteria; to the informed consent process; to intervention delivery; to training in Good Clinical practices (GCP) and regulations pertaining to the Conduct of Human Participant Research for study personnel; to routinely scheduled study contact with enrolled participants; to protocol fidelity monitoring; to the real time review of AEs; and oversight of MUSC's IRB-procedures for examining study safety are consistently afforded throughout the study. Specific procedures include:

- Participant screening using established inclusion/exclusion criteria per the protocol.
- Full disclosure of all known risks and the possibility of risk from study participation to participants during the informed consent process. Note these risks are minimal.
- Participants will be informed to notify the researchers of any/all suspected or experienced adverse events whether the event is believed to be related or not to the intervention.
- PI or PC will track all reported AE through to resolution.
- All members of the research team will maintain CITI and GCP training.
- PI or PC will maintain weekly contact with all participants to enquire about AE's, monitor study progress, compliance, and safety.
- Participant study logs will be reviewed by the PI or PC to monitor for fidelity compliance with the intervention.
- Quarterly internal quality control audits by the PI or PC of all participant records are planned to ensure compliance with MUSC IRB regulations. The PI and PC will collaborate to resolve any identified errors.
- MUSC IRB and ORI will monitor Investigator compliance and performance.

Minimizing Research-Associated Risk. Study safety monitoring will be conducted by the PI and members of the research team throughout the conduct of this study in compliance with MUSC IRB's continuing review process:

- Tracking and follow-up of participant accrual including withdrawn consents will minimize risk by identifying, disclosing, and mitigating any potentially unknown risk(s) of harm to study participants.
- Timely and appropriate reporting of informed consent process deficiencies, protocol deviations, privacy breaches, conflicts of interest, and/or changes in personnel.
- Ongoing soliciting, monitoring, and appropriate reporting of adverse event activities.
- Timely and appropriate IRB submission of safety-related documents such as audit reports, sponsor progress reports, ISM reports, and other materials or communications that might impact the safe conduct of this study.
- Active cooperation with the IRB, ACO, sponsor, and other applicable entities in the event of a random or for-cause internal or external audit.

